### v. Determination of Patients/Data for Analysis

The ITT cohort will be used to analyzed this objective. The PP cohort may be used to analyze this objective as a supplementary analysis.

#### vi. Subgroup Analyses

Subgroup analysis for subjects with small vessel disease stroke and large vessel cervical or intracranial atherosclerosis stroke will be presented. See section 7.9 for details.

### **Secondary Objective**

To compare the incidence rates of AF through the duration of study follow-up between study arms

### i. Hypothesis

H0:  $h_C(t) = h_T(t)$  for t > 0 months

HA:  $h_C(t) \neq h_T(t)$  for t > 0 months

where  $h_T(t)$  and  $h_C(t)$  are the hazard functions of first detected and adjudicated AF at time t for subjects with and without the Reveal LINQ diagnostics for AF, respectively. Hazard functions and survival functions are transformations of each other.

### ii. Endpoint Definition

AF will be defined as an AF event lasting more than 30 seconds. The first AF episode detected and adjudicated by the endpoint adjudication committee will be used for this analysis. This is the same definition used for the primary objective.

### iii. Performance Requirements

This secondary objective will be tested in a hierarchical fashion. This means that if the primary objective is met, then this secondary objective will be tested. The null hypothesis will be rejected if the two-sided log-rank test p-value is less than 0.05.

This document is electronically controlled. Printed copies are considered uncontrolled.

### 056-F286, Statistical Analysis Plan Template, Version 2.0

### iv. Analysis Methods

Arrhythmic episodes recorded by the subject's inserted/implanted device or from external monitoring will be adjudicated by the adjudication committee to determine if they meet the secondary endpoint definition. Only first detected and adjudicated AF episodes during all follow-up will be included for analysis. Each subject's time to first detected and adjudicated AF will be defined as the time from randomization date to the date of first documented AF (i.e. the date of event per Reveal LINQ ICM, ECG, etc.) to meet the secondary objective endpoint definition.

Each subject's time to first detected and adjudicated AF will be defined as the time from randomization date to the date of first documented AF (i.e. the date of event per Reveal LINQ ICM, ECG, etc.) as in the secondary endpoint definition above, and Kaplan-Meier curves will be generated for each randomization arm. Subjects who have not experienced an AF endpoint through the duration of the study follow-up will be censored at their point of last contact, usable Reveal LINQ ICM interrogation or CareLink transmission, whichever is later.

A two-sided log-rank test will be performed to compare the rates between arms. Survival estimates with 95% confidence intervals will be reported for each arm. The hazard ratio estimate for the treatment effect with its 95% confidence interval will be reported.

The types of monitoring (i.e., wired monitor, wireless monitor, etc.) used to identify AF events in the control arm may be reported to further characterize the events.

### v. Determination of Patients/Data for Analysis

The ITT cohort will be used to analyze this objective. The PP cohort may be used to analyze this objective as a supplementary analysis.

### vi. Subgroup Analyses

Subgroup analysis for subjects with small vessel disease stroke and large vessel cervical or intracranial atherosclerosis stroke will be presented. See section 7.9 for details.

### 7.10. Safety Evaluation

Relatedness of adverse events using the CEC adjudication will be summarized using counts and percentages. Seriousness of adverse events using the Medtronic classification will be summarized using counts and percentages. Details of individual adverse events will be listed.

This document is electronically controlled. Printed copies are considered uncontrolled.

Version 2.0 15/MAY/2017

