5.1.1. Minimization of Bias

Selection of subjects, treatment of subjects, and evaluation of study data are potential sources of bias. Methods incorporated in the study design to minimize potential bias include (but are not limited to):

• Subjects will be screened to confirm eligibility for enrollment with defined inclusion/exclusion criteria prior to enrollment.

18 December 2018 Version 4.0 Page 18 of 66

- Subjects will be randomized 1:1 to the continuous monitoring arm vs control arm
- Demographics and medical history will be collected at baseline in order to later assess possible characteristics that may influence endpoints.
- To ensure a widespread distribution of data from study sites, no more than 10% of total expected enrollments (50 subjects) may come from a single site.
- It is recommended that all patients at an investigational site with a recent ischemic stroke of presumed known origin be screened for the study.
- All study site and Medtronic personnel will be trained using standardized training materials.
- Regular monitoring visits will be conducted to verify adherence to the Clinical Investigation Plan and source data.
- An independent clinical events committee (CEC) will be utilized to regularly review and adjudicate reported adverse events and recurrent stroke/TIAs.
- An independent committee will adjudicate AF episodes. The committee will be comprised of
 individuals experienced with identifying AF will review the device EGM records to ensure AF was
 appropriately identified.

In summary, potential sources of bias that may be encountered in this clinical study have been considered and minimized by careful study design.

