10.2.2. Adverse Events and Deficiency Classification

All reported AEs and DDs will be reviewed by a Medtronic representative. AEs will be classified according to the definitions provided.

Upon receipt of AEs at Medtronic, a Medtronic representative will review the AE/DD for completeness and accuracy and when necessary will request clarification and/or additional information from the Investigator. Medtronic will utilize MedDRA, the Medical Dictionary for Regulatory Activities, to assign a MedDRA term for each adverse event based on the information provided by the investigator.

Regulatory reporting of AEs and DDs will be completed according to local regulatory requirements. Refer to Table 12 and Table 13 for a list of required investigator and Medtronic reporting requirements and timeframes. It is the responsibility of the investigator to abide by any additional AE reporting requirements stipulated by the Ethics Committee responsible for oversight of the study.

For emergency contact regarding a SAE, contact a clinical study representative immediately (refer to the study contact list provided in the site's study documents binder/investigator site file or refer to the contact information provided on the title page).

Adverse Events and Deaths will be classified according to the standard definitions as outlined below:

18 December 2018 Version 4.0

Page 44 of 66

Table 7: Adverse Event Classification Responsibilities

What is classified?	Who classifies?	Classification Parameters
Deletedeses	Investigator	Procedure RelatedSystem Related
Relatedness	Sponsor	Procedure RelatedSystem RelatedCardiovascular Related
	Investigator	SAE
Seriousness	Sponsor	SAE, Complication or Observation (for all system or procedure related adverse events)
Diagnosis	Investigator	Based on presenting signs and symptoms and other supporting data
Diagnosis	Sponsor	MedDRA term assigned based on the data provided by Investigator
Death Classification	Investigator	Sudden Cardiac, Non-sudden Cardiac, Non-Cardiac, Unknown

An independent Clinical Events Committee (CEC) will at minimum conduct a medical review of all endpoint related events for subjects participating in the study. Additionally, the CEC will provide an adjudication of the death classification for all reported deaths.

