11.1. Clinical Events Committee (CEC) Review

At regular intervals, an independent Clinical Events Committee (CEC) will at minimum conduct a medical review (adjudicate) of reported arrhythmias including AF episodes/events as well as reported strokes/TIAs and deaths for subjects participating in the study.

The CEC will consist of a minimum of three (3) non-Medtronic employed physicians that are not participating investigators for the study, including a CEC chairperson. At least three CEC members must adjudicate, at a minimum, all deaths and endpoint related events. All other AEs may be adjudicated by at least one physician member of the CEC.

Medtronic personnel may facilitate and participate in a CEC meeting but will be non-voting members.

18 December 2018 Version 4.0 Page 49 of 66

Medtronic

For adverse events and deaths reviewed by the CEC, Medtronic will provide the CEC with the Investigator's description and classification. The CEC is responsible for reviewing the Investigator's assessment and supportive documentation (when available), reviewing applicable definitions, and determining final classifications for all adjudication parameters. Additionally, the CEC will provide an adjudication of the death classification for all reported deaths including primary cause of death.

If the CEC disagrees with the investigator's classification of the event, the rationale will be provided to the investigator. If the investigator agrees with the CEC's adjudication, the case report form documenting the AE will be updated accordingly.

If the investigator does not agree with the CEC's adjudication classification, both determinations will be provided within the final report; however the CEC's adjudication will be used for data analysis. The disagreement will also be included in reporting to ethic committees and regulatory authorities, if required.

12. Statistical Design and Methods

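### SAP 7.10 tabulates adverse-event seriousness from the sponsor's classification, which does not fit the protocol's rule that the CEC's adjudication is the one analysed; the protocol does not itself settle whose value counts

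*SAP*

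**What the plan says.** SAP 7.10 uses two sources in consecutive sentences. On relatedness: "Relatedness of adverse events using the CEC adjudication will be summarized using counts and percentages". On seriousness: "Seriousness of adverse events using the Medtronic classification will be summarized using counts and percentages". It gives no reason for the change. It adds that individual events will be listed in detail, but not which party's classifications the listing will carry.

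Protocol 11.1 describes how the CEC handles the adverse events and deaths it reviews. The sponsor gives it the investigator's description and classification, and the CEC is responsible for "determining final classifications for all adjudication parameters". If the investigator still disagrees, both views go into the final report; "however the CEC's adjudication will be used for data analysis". Protocol 5.1.1, on minimising bias, cites an independent CEC that "will be utilized to regularly review and adjudicate reported adverse events and recurrent stroke/TIAs".

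Protocol 10.2.2, Table 7, sets out who classifies what. For seriousness, the investigator classifies SAE status, and the sponsor's entry reads "SAE, Complication or Observation (for all system or procedure related adverse events". The table has no CEC entry.

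Protocol 5.1 describes the study as non-blinded, and Protocol 12 has the sponsor's own staff or appointees carry out all analyses.

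**The concern.** Up to three parties may hold a view on whether an event was serious: the investigator, the sponsor and the CEC. SAP 7.10 sends only the sponsor's view to the table. The sponsor makes the device and does the analysis, and nobody is blinded to arm. The protocol set up an independent committee to limit this kind of exposure, and the SAP relies on that committee for relatedness but not for seriousness.

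At stake is the credibility of the SAE and complication counts for the inserted device and, for cardiovascular events, which are collected in both arms, the comparison of SAE counts between arms. If sponsor and investigator differ on an event, the table would not show it, and the listing is not required to.

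**Working it through.** No sample-size or power figure is involved, so the check is mainly a comparison of texts.

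**1. Which source does each document point to?**

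| Item | SAP 7.10 | Protocol Table 7 | Protocol 11.1 |
|---|---|---|---|
| Relatedness | CEC | Investigator and sponsor | CEC final on its parameters, which are not listed |
| SAE status | Sponsor | Investigator and sponsor | As above |
| Complication or Observation | Sponsor | Sponsor only | As above |
| Death classification | Not stated | Investigator | CEC |

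**2. Does Protocol 11.1 reach seriousness?** What the CEC reviews is the investigator's classification. Under Table 7, and under Protocol 10.1.1 on the adverse event form, that includes seriousness. What it produces is a final classification on every adjudication parameter. The natural reading is that SAE status is included. But 11.1 never lists the parameters, so this is an inference and not a stated rule.

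**3. Does Table 7 authorise the SAP's choice?** It gives the sponsor a seriousness classification, so SAP 7.10 may have been written from it. But the table says who classifies, not whose value is analysed. Its silence about the CEC carries little weight: it has no CEC entry for relatedness, yet SAP 7.10 uses the CEC there, and none for death, yet the text below the table, Protocol 10.3.1.2 and Protocol 11.1 all have the CEC adjudicate deaths. Because the table also has the investigator classify SAE status, it gives no ground for preferring the sponsor's value.

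**4. What is outside the problem?** Attribution to system or procedure comes from the CEC under SAP 7.10. The primary and secondary objectives concern adjudicated AF and use no seriousness data.

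**5. Size.** The documents give no rate of device-related events, so this is only an illustration.

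- Subjects in the device arm: 486 / 2 = 243.
- One subject reclassified: 1 / 243 = 0.4 percentage points. Two: 2 / 243 = 0.8 percentage points.
- Assume that 1% to 3% have a serious system- or procedure-related event: 243 × 0.01 = 2.4 and 243 × 0.03 = 7.3, or about 2 to 7 subjects. One reclassification then changes the count by between 1/7 = 14% and 1/2 = 50%.

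This shows that a small count is sensitive to single decisions. It does not show that any misclassification is likely.

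**The case against.** The strongest reply is that SAP 7.10 simply follows Table 7, which expressly gives the sponsor a seriousness classification. The sentence in Protocol 11.1 about which adjudication is analysed settles disputes between CEC and investigator; it mentions neither the sponsor nor seriousness. This stands to the extent that a reader might infer a plain contradiction between SAP and protocol. The documents do not support that: the inconsistency also lies inside the protocol, between Table 7 on one side and 5.1.1 and 11.1 on the other.

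Second, the criteria for SAE and Complication are largely factual: death, hospitalisation, invasive intervention. That limits discretion without removing it, since serious deterioration and life-threatening illness call for judgement. Third, for device-related events knowledge of the arm adds little, because they arise only in people who have the device. That is right, though not for cardiovascular events. Fourth, no safety hypothesis is tested and the devices are already marketed. This limits the importance of the point but does not say whose value to tabulate.

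A reader might also infer that device events could lack any CEC relatedness value, because Protocol 11.1 says: "All other AEs may be adjudicated by at least one physician member of the CEC". The preceding sentence requires at least three members for deaths and endpoint events, so this is more probably a smaller quorum than optional review. Protocol 5.1.1, and the opening of Protocol 11, which gives the CEC the assessment of adverse events, point the same way.

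**Conclusion.** The point holds as an unresolved conflict over the data source for the seriousness tables. SAP 7.10 sets a definite rule, the sponsor's value, and that rule does not fit Protocol 11.1 or the safeguard in Protocol 5.1.1. Table 7 does not resolve it, because it names two classifiers and no order of precedence. The conclusion rests on reading the adjudication parameters in 11.1 as including seriousness, which is likely but unstated. If they do not, the gap remains: nothing in the documents explains why the sponsor's SAE call displaces the investigator's.

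A reader might go further and infer that the manufacturer judges its own device's harms throughout. The documents do not support this. Attribution is taken from the CEC, the investigator also classifies SAE status, and nothing suggests that events would be downgraded. Nor is a bias of any particular size shown: the 14% to 50% range rests wholly on the assumed event rate. The point is worth correcting because it is cheap to correct and concerns the independence of a safety table in a non-blinded trial.

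**What to change.** **SAP 7.10**

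- Tabulate SAE status by the CEC's final classification where the event was adjudicated, and otherwise by the investigator's.
- Tabulate Complication or Observation by the CEC's classification where adjudicated, and otherwise by the sponsor's, labelled as the sponsor's. This fallback differs because Table 7 gives that classification to the sponsor alone; without it, events the CEC has not classified would have no value.
- List every event for which the investigator, sponsor and CEC values differ, showing all of them.

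**Protocol 11.1 and Table 7**

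- Name relatedness and seriousness as CEC parameters for system- and procedure-related adverse events.

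The SAP states that it was written from Version 2 of the protocol, and the current protocol is Version 4.0, so the change can be made when the two are aligned. The cost is a few sentences, slightly more form work for a committee that already exists, and the approvals that Protocol 14.6 requires for a protocol revision. The SAP change can be made without waiting for them. The SAE count may come out slightly less favourable.

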### 7.11. Health Outcomes Analyses

Health outcomes will be compared between study arms using the EQ-5D questionnaire and symptoms collected in the symptoms assessments.

### 7.12. Changes to Planned Analysis

Any changes to the data analysis methods described in the CIP and this Statistical Analysis Plan, and the justification for making the change, will be described in the clinical study report. Additional exploratory analyses of the data will be conducted as deemed appropriate.

# 8. Validation Requirements

Minimum validation requirements for the programs written to execute the analyses in this SAP:

- Primary objective: Level I (independent program)
- Secondary objective: Level II (peer review)
- AE tables and listings: Level II (peer review)
- Deviation table and listing: Level II (peer review)
- Patient disposition flowchart numbers: Level II (peer review)
- Other programs needed for final report analyses not specified: Level II (peer review)

Programs previously validated at Level I or Level II further modified with minor changes may be validated at Level III.

It is expected that Standard Operating Procedures will be followed for other programs that effect the programs written to execute the analyses in this SAP, such as data retrieval programs, dataset mapping programs, analysis dataset programs, etc.

This document is electronically controlled. Printed copies are considered uncontrolled.
